#### **IV. DATA COLLECTION**

Collected data will include age, gender, race, ethnicity, verbal pain rating scale, headache/migraine frequency and use of headache symptomatic medications.

#### **V. DATA ANALYSIS**

Sample size determination was calculated based on a minimally significant mean difference in verbal pain score of 1.5. To detect this difference with 90% power, alpha = .05; a total of 70 subjects (35 per group) will be required (SD=1.9). T-tests will be used to compare outcome of both groups. Statistical analysis will be carried by GB.

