## I. BACKGROUND AND SIGNIFICANCE

Chronic migraine (CM) is a complex, progressive headache disorder affecting approximately 1.3-2.4% of the general adult population. Onabotulinumtoxin type A (BoNTA) is considered an effective, FDA-approved, prophylactic treatment. Injections are administered at 31 sites of the head and neck, and treatment is repeated every 3 months. [2]

BoNTA is manufactured as powder that requires reconstitution with normal saline prior to injection. The manufacturer of botulinum A exotoxin (Allergan Inc) has historically encouraged reconstitution with unpreserved saline. [3] However, the use of preserved saline (i.e. bacteriostatic) is common among practitioners to lengthen the shelf life of BoNTA (Botox ®) after reconstitution.

A growing body of literature on the cosmetic use of BoNTA has suggested that preserved saline exerts a local anesthetic effect, and reduces the procedure discomfort when used in reconstitution in lieu of preservative-free saline. [3,4,5,6] However, this has never been studied in chronic migraine, and while reducing discomfort is a desirable target in all procedures, it has a special importance for the use of BoNTA in chronic migraineurs due to the numerous injection locations each session (31 sites) and the ubiquity of scalp tenderness in this population. [7] In addition, the pain during procedure is a known migraine trigger for many of these patients. In fact, one study showed that up to 5% report migraine attacks lasting more than 5 days as a side effect of BoNTA injection. [8]

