#### D. Study Procedures

UHCC headache clinic performs 20-25 BoNTA injections a week on average. Enrollment plan is as following: on weekly basis, one of the investigators, either SH or AF, will contact all patients scheduled for BoNTA injections and explain the study's objectives and details. If the subject agrees to enroll, he/she will be assigned a study serial number and will be randomized to one of the two groups. Randomization will be done through a simulated "coin flipper" website; [www.random.org](http://www.random.org). Heads will be assigned to the preserved saline group, and tails will be assigned to the preservative-free saline group. SH and AF will keep the assignment sheet in a password-protected excel file that only they have access to.

On the day of the procedure, informed consent will be confirmed and signed. Then, each subject will receive 10-15 minute session on the appropriate use of headache diary.

Same randomizing investigator will reconstitute BoNTA vial (Allergan Inc) using one of the two identical solutions, and then hand it to the principal investigators; AZ or LM, who will be

performing the procedure using 30G 1/2' needles. AZ ,LM, and the subject will all be blinded to which solution is used for reconstitution.

Following the injections, subjects will be asked to rate procedure-related pain using verbal pain rating scale (0 to 10). They will be asked to maintain a 7-day headache diary (see supplementary). Prepaid mail envelopes will be provided to ensure the return of the diaries following their completion.

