#### **VI. ETHICAL CONSIDERATIONS**

##### **A. Informed Consent**

Informed consent will be obtained by investigators SH or AF at the time of the visit. Refusal of participation will not affect the treatment plan, and the subject will continue to receive BoNTA injections as scheduled, using the standard preservative-free saline.

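### Should the plan have taken a pain rating before the injections and adjusted for it, instead of using a plain t-test?

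*Combined protocol and SAP*

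**What the plan says.** Section V sizes the trial on the verbal pain score: difference 1.5, SD 1.9, 90% power, alpha .05, 35 subjects per group. On the analysis it says that "T-tests will be used to compare outcome of both groups". It names no covariate.

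Section III.D places the pain rating after the procedure: "Following the injections, subjects will be asked to rate procedure-related pain using verbal pain rating scale (0 to 10"). Before injection on the day it lists only confirmation of consent and training on the headache diary. Section IV gives the data items: "Collected data will include age, gender, race, ethnicity, verbal pain rating scale, headache/migraine frequency and use of headache symptomatic medications". That is one verbal pain item, and no pre-injection rating is described. The diary form and the appendices are not shown and headache frequency has no stated timing, so a baseline headache item cannot be fully excluded.

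On blinding, Section III.D says that both injectors and "the subject will all be blinded to which solution is used for reconstitution". The person who randomizes knows the allocation and also prepares the vial.

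**The concern.** In a trial with a continuous outcome, a baseline measure that predicts the outcome can be used in an analysis of covariance (ANCOVA) to narrow the confidence interval without enrolling anyone else. Section I offers a candidate when it refers to "the ubiquity of scalp tenderness in this population": a subject whose head or scalp is already sore may find the injections more painful. Here nothing of the kind is recorded, and the state just before injection cannot be recovered later. If such a rating predicted the score well, the trial would be giving up precision on the one comparison that sets its sample size. At stake is the width of the interval and some power. Bias and type I error are not in question.

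**Working it through.** **Inputs.** From Section V: difference 1.5, SD 1.9, alpha .05, 35 per group. Two-sided testing is inferred, because it reproduces the stated size and one-sided testing does not (29 per group). The correlation r between a pre-injection rating and the post-injection score is not in the documents; 0 to 0.5 is assumed.

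**1. The plan's own figure.** The standard error of the difference is 1.9 × √(2/35) = 0.454, and the noncentrality is 1.5/0.454 = 3.30 on 68 degrees of freedom. Power from the noncentral t distribution is 90.2% at 35 per group and 89.4% at 34. So 35 is the smallest group size that reaches 90%, as stated. The 95% half-width is 1.995 × 0.454 = 0.906.

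**2. With one covariate.** The residual SD is 1.9 × √(1 − r²), the degrees of freedom fall to 67, and the variance of the difference is inflated on average by 1 + 1/66 because the slope must be estimated.

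| Assumed r | Residual SD | Power | 95% half-width |
|---|---|---|---|
| no covariate | 1.900 | 90.2% | 0.906 |
| 0 | 1.900 | 89.8% | 0.913 |
| 0.1 | 1.890 | 90.1% | 0.909 |
| 0.2 | 1.862 | 90.9% | 0.895 |
| 0.3 | 1.812 | 92.3% | 0.871 |
| 0.5 | 1.645 | 96.2% | 0.791 |

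Break-even is at r of about 0.12. The gain is 90.9 − 90.2 = 0.7 points at r = 0.2 and 92.3 − 90.2 = 2.1 points at r = 0.3.

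**3. What the gain is worth in subjects.** Unadjusted power is 91.0% at 36 per group and about 92.5% at 38. The gain at r = 0.2 therefore equals about 2 × (36 − 35) = 2 more subjects, and at r = 0.3 about 2 × (38 − 35) = 6. Section III.D reports 20-25 injections a week at the clinic, so even 6 is a small number.

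**4. What would cancel it.** A narrower interval does not help if the extra question also pulls the two groups' scores together. Power is roughly unchanged when the difference shrinks in proportion to the half-width:

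- r = 0.2: 1.5 × (1 − 0.895/0.906) = 0.02 points
- r = 0.3: 1.5 × (1 − 0.871/0.906) = 0.06 points
- r = 0.5: 1.5 × (1 − 0.791/0.906) = 0.19 points

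Section VI.B acknowledges that drawing attention to pain and asking subjects to report it may raise the discomfort. A 0-10 question on head pain shortly before a 0-10 question on injection pain could anchor the second answer to the first. With a blinded asker this should not favour one group, but it could still shrink the difference. The documents give no estimate of the effect. At r = 0.2, a shrinkage of 0.02/1.5, or about 1%, is enough to cancel the gain.

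**5. Is there reason to expect a large r?** Section I says scalp tenderness is widespread. It does not say that its severity varies between patients or that it predicts injection pain. A feature that nearly everyone shares is not, for that reason alone, a strong predictor.

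**The case for a change.** The best case for the extra rating has three parts.

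- **The omission is irreversible and the payoff looks lopsided.** At most 90.2 − 89.8 = 0.4 points of power are lost if r = 0, against 96.2 − 90.2 = 6.0 points gained at r = 0.5.
- **The SD has no stated source.** If it were 2.3 (an assumption), unadjusted power would be 76.7%, and adjustment would bring it to 79.9% at r = 0.3 or 86.9% at r = 0.5.
- **It can be done without bias.** Because "he/she will be assigned a study serial number and will be randomized to one of the two groups" before the visit, the rating would come after randomization. A blinded injector could still collect it from a blinded subject before any injection.

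The arithmetic stands, and so does the point on feasibility. The lopsided payoff does not, because the 0.4-point loss counts only the cost of estimating a useless covariate. It leaves out any effect of the question on the later rating, which at modest r could exceed the gain. Asking the injector to collect it has a further drawback: learning how tender the subject is just beforehand might change how the injections are given and add noise, equally in both groups.

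The SD point is a fair caution about the sample size, but it does not show that the chosen analysis is wrong. At r = 0.3 adjustment would recover only 79.9 − 76.7 = 3.2 points.

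**Conclusion.** The concern does not hold. The t-test is valid under randomization, 35 per group follows exactly from the stated inputs, and no statement in the protocol conflicts with taking a single post-injection rating. Adding a pre-injection rating and an ANCOVA is an option on which statisticians may reasonably differ. Its benefit is nil below about r = 0.12 and small up to about r = 0.3. Its net sign at modest r is unknown, because the protocol itself expects that asking about pain can affect the answer. Only a correlation near 0.5, for which the documents give no support, would make the gain substantial.

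This conclusion covers the pain score only. The 90.2% assumes SD 1.9 and an even 35/35 split; averaged over the splits that a simple coin toss of 70 subjects can produce, power is 89.8%. Nothing here speaks to the power for headaches in the following week, for which Section V gives no calculation.

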### **III. METHODS**

#### **A. Study Design**

The study is a prospective, randomized, double-blind trial.

Subjects will be enrolled consecutively at UHCC headache clinic from the practice of the two lead authors; AZ and LM who will be performing the injections.

Two of the investigators, SH or AF, will perform the randomization through simulated, web-generated, coin toss.

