#### **C. Study Population**

- Patients with diagnosis of chronic migraine receiving FDA-approved treatment with BoNTA injection as per standard protocol used in PREEMPT study [2]. Standard protocol consists of 31 injection sites, with total dose ranging from 155 u to 195u.
- Exclusion criteria:
  1. Age < 18, or > 79
  2. Subjects whom BoNTA injections deviate from standard protocol for any reason, such as head/neck infection, head deformity, recent surgery...etc.
- Study population will be randomized into two groups; preserved saline and preservative-free saline

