#### G. Subject Privacy and Data Confidentiality

Information about study subjects will be kept confidential and managed according to the requirements of the Health Insurance Portability and Accountability Act of 1996 (HIPAA).

A regulatory binder will be maintained for this study. This will include items such as this protocol, the letter of approval from the IRB, the consents, and all other information pertinent to this study. The investigators will permit study-related monitoring, audits, and inspections by the SUNY Upstate IRB, the sponsor and government regulatory bodies of all study related documents (e.g. source documents, regulatory documents, data collection instruments, study data etc.).

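### Two physicians give the injections: does the pain comparison need to record and adjust for which of them injected?

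*Combined protocol and SAP*

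**What the plan says.** Section III.A (Study Design) names two injecting physicians as the source of patients: "Subjects will be enrolled consecutively at UHCC headache clinic from the practice of the two lead authors". Section III.D (Study Procedures) has one or the other treat each subject, blinded to the solution, and then collects the outcome: "Following the injections, subjects will be asked to rate procedure-related pain using verbal pain rating scale (0 to 10" on the scale. Allocation is by a simulated coin toss for each subject, with no stratification by physician.

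Section IV (Data Collection) reads: "Collected data will include age, gender, race, ethnicity, verbal pain rating scale, headache/migraine frequency and use of headache symptomatic medications". The injecting physician is not in that list.

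Section V (Data Analysis) sizes the trial on the pain score ("Sample size determination was calculated based on a minimally significant mean difference in verbal pain score of 1.5"), states the number ("To detect this difference with 90% power, alpha = .05; a total of 70 subjects (35 per group) will be required (SD=1.9") and fixes the test: "T-tests will be used to compare outcome of both groups". No covariate is named.

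The procedure is standardised. Section III.C (Study Population) says "Standard protocol consists of 31 injection sites" and excludes patients whose injections depart from it. Section III.B (Study Materials) fixes the dilution volume and syringes, and Section III.D fixes the needle.

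**The concern.** A score for pain caused by a procedure may well depend on who performs it. Technique differs between physicians, and so may their patients. With two injectors, a coin toss that ignores them, no named data field and no model term, two worries arise. Chance imbalance of injectors between arms might distort the treatment difference, and variation between injectors might inflate the standard error needlessly. If either were material, the trial could give a misleading or less precise answer, and any later adjustment would be chosen after the data were seen. The apparent remedy is small: one field and one degree of freedom.

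**Working it through.** **Inputs from Section V:** difference 1.5, SD 1.9, alpha 0.05 (taken as two-sided), power 90%, 35 per group. **Assumed, because the documents give neither:** the difference D in mean pain between the two injectors, and one injector's share q of the patients. Total SD is held at 1.9.

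**1. The plan's own number.** Normal approximation: n per group = 2 × (1.960 + 1.282)² × 1.9² / 1.5² = 33.7, so 34. By the exact t calculation, the standard error at 35 per group is 1.9 × √(2/35) = 0.454 and the noncentrality is 1.5/0.454 = 3.30. That gives power 90.2%, against 89.4% at 34 per group. The 35 per group is reproduced for the unadjusted two-sided t-test. Averaged over the unequal arms a coin toss can produce, power with 70 subjects is about 0.898.

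**2. Validity.** Subjects are randomised individually and the injectors do not know the solution, so nothing in the plan links injector to arm. With n = 70 and coin-toss allocation, simulated type I error is 0.049 to 0.051 with or without an injector term.

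**3. Chance imbalance.** With q = 0.5, the gap in injector share between arms has SD √(0.25 × 2/35) = 0.12. At D = 1 the estimate therefore shifts with SD 0.12 points. The t-test's standard error is about 1.819/(2 × 1.995) = 0.456. The shift contributes (0.12/0.456)² ≈ 7% of its variance. Injector's share of the outcome variance at D = 1 is the same: 0.25/3.61 = 6.9%. The unadjusted standard error already contains this component.

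**4. Gain or loss from a model term.** Unadjusted power is about 0.898 throughout. Adjusted results by simulation, with equal caseloads unless stated:

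| D (points) | Share of variance, D²/4 ÷ 3.61 | Adjusted power | Adjusted power, 70/30 caseload | Mean 95% CI width (unadjusted 1.819–1.820) | Adjusted CI is the narrower |
|---|---|---|---|---|---|
| 0 | 0% | 0.894 | 0.894 | 1.833 | 20% |
| 0.25 | 0.4% | 0.895 | 0.895 | 1.830 | 26% |
| 0.5 | 1.7% | 0.899 | 0.899 | 1.817 | 42% |
| 0.75 | 3.9% | 0.905 | 0.904 | 1.797 | 61% |
| 1.0 | 6.9% | 0.913 | 0.910 | 1.769 | 79% |
| 1.5 | 15.6% | 0.937 | 0.930 | 1.685 | 97% |

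The break-even can be checked by hand. At D = 0 the width ratio squared is (1.833/1.819)² = 1.015, so the term costs about 1.5% of variance through the lost degree of freedom and the chance correlation of injector with arm. To recover that, D²/4 must be about 0.015 × 3.61, so D = √(4 × 3.61 × 0.015) ≈ 0.47.

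**5. Expected gain under modest differences.** With equal caseloads the power change is −0.44 percentage points at D = 0 (0.8936 − 0.8980) and +1.59 at D = 1 (0.9131 − 0.8972). It is roughly −0.44 + 2.03 D²; at D = 0.5 this gives +0.07 against +0.06 simulated. If D is half-normal with scale s, the mean of D² is s². The average change is then −0.44 + 2.03 × 0.09 = −0.26 points at s = 0.3, and −0.44 + 2.03 × 0.5625 = +0.70 points at s = 0.75. At a 70/30 caseload (−0.43 at D = 0, +1.26 at D = 1) the same steps give −0.28 and +0.52.

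**The case for a change.** The strongest case for a change is asymmetry. The most the term can be expected to lose is about 0.4 percentage points of power, worth about one subject. The gain is worth about four subjects at a 1-point difference and eleven at 1.5. Fixing dilution, sites and needle does not fix hand technique or the mix of patients in each practice. Recording the injector would also let the split by arm be described, and naming the term in advance would prevent a choice made after seeing the data.

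The arithmetic stands, and so does the fact that neither Section IV nor Section V names the injector. The rest is weaker:

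- The gains sit in the upper half of an assumed range that nothing in the documents supports. D = 1 is an injector effect two-thirds as large as the treatment effect the trial is sized for; D = 1.5 equals it.
- A closed-form calculation looks kinder to adjustment (90.2% at D = 0, 92.1% at D = 1), but it ignores the chance correlation between arm and injector. Simulation with 35 per group fixed gives about 89.8% and 91.7%, against 90.2% unadjusted.
- The pre-specification point is already met. Section V commits to an unadjusted t-test, so no adjustment decision is left open.
- The data list is not exhaustive: it omits even the treatment group. Section VI.G provides for keeping "all study related documents (e.g. source documents, regulatory documents, data collection instruments, study data etc", so the injector may well be recoverable. An unnamed field is missing detail; it does not show that the item goes unrecorded.
- The same plausibility argument would apply to age and gender, which are collected. Nothing shows that injector predicts pain better.

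**Conclusion.** The concern does not hold. The planned t-test is unbiased, keeps its nominal error rate and has the sample size it needs; chance imbalance of injectors is already within its standard error. An injector term would affect precision only: a loss of about 0.4 percentage points of power if the injectors are alike, nothing near 0.5 points, and a gain of about 1.6 at 1 point. Averaged over modest assumed differences, the change runs from about −0.3 to +0.7 percentage points.

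These figures rest on 70 subjects allocated by coin toss, a true difference of 1.5, a total SD of 1.9, and injector differences and caseloads that are assumed throughout. A documented injector difference well above half a point would make adjustment worth having, but even then the planned analysis would remain valid. On what the documents give, choosing the plain t-test is a reasonable design decision on which statisticians may differ.

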#### **VI. ETHICAL CONSIDERATIONS**

##### **A. Informed Consent**

Informed consent will be obtained by investigators SH or AF at the time of the visit. Refusal of participation will not affect the treatment plan, and the subject will continue to receive BoNTA injections as scheduled, using the standard preservative-free saline.

##### **B. Risks and Side Effects**

Both solutions of normal saline are widely used in practice, and there are no known risks or side effects from using either.

Alerting subjects to the painful nature of the procedure and asking them to report that pain may exaggerate the resulting discomfort. Yet, we do not anticipate the discomfort to be sufficient to produce a significant clinical distress. The study carries inherent inconvenience related to filling headache diaries.

#### C. Benefits to Subjects

None

#### D. Costs to Subjects

None

#### E. Compensation to Subject

None

#### F. Provisions for vulnerable subjects

BoNTA injections is contraindicated in children <18 year-old, and in pregnancy. UHCC headache clinic does not participate in prisoners care. Thus, the study will not include vulnerable subjects.

#### G. Subject Privacy and Data Confidentiality

Information about study subjects will be kept confidential and managed according to the requirements of the Health Insurance Portability and Accountability Act of 1996 (HIPAA).

A regulatory binder will be maintained for this study. This will include items such as this protocol, the letter of approval from the IRB, the consents, and all other information pertinent to this study. The investigators will permit study-related monitoring, audits, and inspections by the SUNY Upstate IRB, the sponsor and government regulatory bodies of all study related documents (e.g. source documents, regulatory documents, data collection instruments, study data etc.).

## VIII. APPENDICES
